## **V. STUDY PRODECURES**

This is a single site study. Participation will last 6 months (see Figure 2), and entails:

- Completing a scripted onboarding call (approximately 30-45 minutes)
- Making a quit attempt
- Engaging with smoking cessation support (randomized) over the course of seven weeks, one week prior and 6 weeks following the originally chosen quit day

- Completing five online, REDCap-administered surveys, administered prior to the quit day (online, as part of a screening test), and at 2-week, 6-week, 3-month, and 6-month follow-ups of the participant's chosen quit day

[figure not shown]
[figure not shown]

Figure 2. Timeline of study participation

After onboarding, participants will be asked to engage with the smoking cessation materials they receive as part of this study (i.e., smartphone apps or written materials) for a period of seven weeks (1 week before, 6 weeks following the quit attempt). They may choose to continue to use these materials thereafter.

#### Treatment Condition: “Smiling Instead of Smoking” (SiS) smartphone app

[figure not shown]
Participants randomized to the treatment condition will be asked to use Version 3 of our “Smiling Instead of Smoking” (SiS) smartphone app for a period of 7 weeks. The SiS app is a smartphone app that engages participants in daily positive psychology habit-building exercises over the course of 7 weeks, as-needed happiness boost activities and ‘behavioral challenges’ every 2-3 days that are designed to engage participants with *ad libitum* tools offered by the app, which offer tracking functionality (i.e., log of smoked cigarettes), graphical summaries (i.e., pie chart of reason smoked for the past 20 cigarettes), reminders (i.e., a tool to send reminders to stay smoke-free at specific times), note keeping (i.e., personal reasons for quitting), distraction (i.e., a game called “Magma Bear”) and information (e.g., benefits of quitting, suggested strategies for specific situations). Along the way, the app also provides participants with information about how positive affect is relevant to quitting smoking and health.

Screenshots from SiS Version 3: (1) a habit-building exercise is assigned, (2) its completion is logged, and (3) science findings are shared to reinforce the value of happiness.

**Conceptual Model.** Our goal in using a positive psychology approach is two-fold: (1) to foster engagement with the app, which delivers tools and information recommended by United States Clinical Practice Guidelines (USCPG) for smoking cessation, and (2) to protect against deficits in positive affect occurring during the quit attempt. Based on previous findings on the role of positive affect in smoking cessation regarding desire to smoke, smoking relapse, self-efficacy, and processing of self-relevant health information, and based on the broaden-and-build theory, we hypothesize that completing the app's happiness exercises should protect against expected decreases in positive affect, and thereby provide smokers with the benefits associated with positive affect, namely, reduced desire to smoke, increased self-efficacy, and greater cognitive readiness to deal with the challenges of smoking cessation.

The SiS app does not collect identifiable information. It asks app users to click buttons to log when they smoke and for what reasons they smoke, and to enter text in text boxes describing their personal reasons for quitting smoking, the circumstances under which they smoke, and to describe their experiences in response to the happiness exercises (e.g., naming three good things they experienced that day; describing something beautiful they saw that day). It uses push notifications to alert app users to new tasks (e.g., new behavioral challenge), remind them of tasks that still need to be completed (e.g., a happiness exercise that still needs to be done), and to notify them of challenging times (i.e., “Smoke Alarms” that app users scheduled for themselves within the app). These push notifications are optional, and can be toggled off. The onboarding script teaches participants how to toggle them on and off.

[figure not shown]

The “Smiling Instead of Smoking” (SiS) smartphone app provides information in graphical format, text, and provides links to outside websites (users need to click “Read More” in the “Owl Wisdoms”, and are warned that clicking that link exits the app). App user’s progress through quitting is tracked with ‘badges’.

### **Control Condition #1: “QuitGuide” (QG) smartphone app**

[figure not shown]
Participants randomized to this control condition will be asked to use the National Cancer Institute’s “QuitGuide” (QG) smartphone app for a period of 7 weeks. This smartphone app is one of two smartphone apps the NCI currently has publicly available for use on their smokefree.gov website. Referral to this website is recommended for treating smokers in healthcare settings. QG is frequently used as a comparison app in smartphone app smoking cessation studies. While QG was not developed specifically for nondaily smokers, it targets both nondaily and daily smokers (i.e., when downloading the app, users are asked to specify their smoking pattern, which includes both nondaily and daily patterns of smoking). Some SiS features have direct analogs in QG; others do not. The onboarding script leads QG users through the QG content in the same order as for SiS, to the degree possible: setting the quit day (SiS & QG), happiness-promoting activities vs. tracking mood and craving (SiS vs. QG), guidance on quitting (via behavioral challenges in SiS, vs. “Learn to Quit” information in QG), logging cigarettes (SiS & QG), strategies for smoking triggers (pie chart in SiS, various graphs in QG), setting reminders (time-based in SiS, time and location based in QG), and as-needed tools (happiness-boost activities, suggested strategies in SiS vs. tips in response to reporting craving or negative affect in QG).

The QG app does not collect identifiable information. Upon install, the app asks app users to click buttons and to use sliders to describe their smoking (e.g., typically number of cigarettes smoked per day) and craving pattern (e.g., time of day of strongest craving). Going forward, it uses buttons to allow users to describe their craving and mood any time as they are engaging in their quit attempt.

The QuitGuide (QG) smartphone app asks app users to track their craving and mood as they quit smoking. In response to their reports, they receive tips and tricks for dealing with these triggers.

The QG app also contains a “Learn to Quit” guide, which largely mimics the information provided in the NCI’s booklet “Clearing the Air”.

The QuitGuide (QG) smartphone app provides information in line with the information contained in the NCI booklet “Clearing the Air”.

The QG app also allows text entry so participants can name their personal reasons for quitting smoking, and so they can journal in response to craving or mood triggers. The content of these textboxes is saved on the client but not the server side of this app, so that app users can see their typed in text (e.g., personal reason for quitting smoking), but the National Cancer Institute’s Smokefree Team does not have a record of this text.

## **Control Condition #2: Treatment as Usual (TAU)**

Participants in the treatment as usual (TAU) condition will be asked to make a naturalistic quit attempt, using any methods they feel might help them. To time-match the onboarding experience of SiS and QG participants, study staff will use an onboarding script to lead TAU participants through the NCI booklet “Clearing the Air”, which encourages activities in the same order as implemented in the SiS behavioral challenges (i.e., reflecting on reasons to quit, informing about benefits of quitting, logging smoking and its triggers, formulating strategies for dealing with triggers). Additionally, “Clearing the Air” provides information on smoking cessation support resources, such as counseling and pharmacological approaches.

At the end of treatment, participants complete an online survey via REDCap. This is our primary study endpoint (see Specific Aims). Participants complete two more online surveys via REDCap, occurring 12 and 24 weeks post-quit, for secondary aims.

Table 1 specifies which data are collected at which time points. Please see attached for specific descriptions of each of these measures.

Table 1. Data Collection Instruments per Time Point

Type of Measure Specific Measure	Timing of Assessment				
	BL	Wk 2	Wk 6	Wk 12	Wk 24
Primary Outcome					
Smoking Self-Efficacy Questionnaire (SEQ-12)	X	X	X	X	X
Secondary outcomes					
Smoking status	X	X	X	X	X
Recent cigarette use	X	X	X	X	X
Client Satisfaction Questionnaire (CSQ-8)			X		
Time spent applying content			X	X	X
Use of smoking cessation strategies			X		
Perceived impact of SiS/QG/TAU on quitting			X		
Appreciation Scale (AS)			X		
(SiS/QG only) Actual app usage - continuously recorded	X	X	X	X	X
(SiS/QG only) Self-reported app usage: weeks -1 to 2		X			
(SiS/QG only) Self-reported app usage: weeks 3 to 6			X		
(SiS/QG only) App likeability & satisfaction			X		
(SiS/QG only) System Usability Scale (SUS)			X		
Other outcomes to be explored in mediational analyses					
Emotional well-being					
PANAS Positive And Negative Affect Schedule (PANAS)	X	X	X	X	X
Happiness single-item measures	X	X	X	X	X
Satisfaction With Life Scale (SWLS)	X	X	X	X	X
Subjective Happiness Scale (SHS)	X	X	X	X	X
Perceived Stress Scale (PSS10)	X	X	X	X	X
Desire to smoke					
Brief Questionnaire of Smoking Urges (QSU)	X	X	X	X	X
Thought action repertoire					
Modified Twenty Statement Test (mTST) - Baseline	X				
Modified Twenty Statement Test (mTST) - Follow-up		X	X	X	X
Processing of self-relevant health information					
Attitudes Towards Smoking (ATS)	X	X	X	X	X

Decisional Balance Inventory For Smoking (DCB-short)	X	X	X	X	X
Single-item pros and cons measures	X	X	X	X	X
Commitment To Quitting Smoking Scale (CQSS)	X	X	X	X	X
Single-item motivation measure	X	X	X	X	X
Descriptors					
Demographics	X				
Mental health diagnoses	X				
Smoking history	X				
Fagerström Test for Nicotine Dependence (FTND)	X				
Previous quit attempts	X				
Recent Quit Methods Used		X	X	X	X
E-cigarette use	X	X	X	X	X
Alcohol use	X	X	X	X	X
Smartphone use	X		X		
Center of Epidemiologic Studies Depression Scale (CES-D-10)	X	X	X	X	X
Generalized Anxiety Disorder Screener (GAD-7)	X	X	X	X	X
Snaith-Hamilton Pleasure Scale (SHAPS)	X	X	X	X	X
Life Orientation Test Revised (LOT-R)	X	X	X	X	X
State Optimism Measure (SOM)	X	X	X	X	X
Brief State Optimism Measure (BSOM)	X	X	X	X	X
Generalized Self-efficacy Scale (GSES)	X				
Personality SIMP	X				
Brief COPE	X	X	X	X	X

As noted in Table 1, in addition to outcome variables, we are also collecting descriptive information to describe the participants in this study on constructs relevant to this study:

- Demographics (at baseline, includes age, gender, ethnicity, race, education level, current student status, current employment status, total family/household income, and rurality of current residence)
- Mental health diagnoses (at baseline, “Has a doctor, nurse, or counselor ever told you that you have a mental or psychological condition?” [yes, no]. If participants select “yes,” they asked to select all that apply from a list of Axis I and II psychiatric disorders, or to specify “other mental health diagnosis.”)
- Smoking history (at baseline, captures estimated number of cigarettes participant smoked in lifetime, age when participant first tried smoking (even one or two puffs), age when participant first smoked an entire cigarette, and whether participant has ever smoked daily)
- Fagerström Test for Nicotine Dependence (FTND), a 6-item questionnaire characterizing level of physiological nicotine dependence. Answer choices are assigned numerical values which can be sum-scored to obtain level of dependence [i.e., very low dependence, low dependence, medium dependence, high dependence, or very high dependence])
- Previous quit attempts (at baseline, captures whether participant has tried to quit smoking before, number of previous quit attempts, and types of quit methods previously used [e.g., group counseling/class, smoking cessation app])
- Recent quit methods used (at follow-up time points, captures any additional quit methods used since participant’s quit day [using the same check-box list as seen in Previous Quit Attempts])
- E-cigarette use (at all time points, captures whether participant has ever used electronic cigarettes, whether participant is currently using electronic cigarettes, number of “bouts” of vaping per vaping day, and number of puffs per “bout” of vaping)

- Alcohol use (at all time points, captures whether participant has drunk alcohol in past 30 days, number of drinks per drinking day, number of days in past 30 days having drunk 5+ drinks per drinking occasion [males], number of days in past 30 days having drunk 4+ drinks per drinking occasion [females], number of weeks in past month having drunk 14+ drinks per week [males], number of weeks in past month having drunk 7+ drinks per week [females], and number of drinks per weekday in past week)
- Smartphone Use (5 item questionnaire captures self-reported frequency of smartphone use over the past 30 days, reason for smartphone use, whether push notifications from study app prompts unrelated smartphone use, whether unrelated smartphone use prompts study app use, and location of study app on smartphone)
- Center of Epidemiologic Studies Depression Scale, 10-item version (CES-D-10), designed to assess degree of depressed mood [e.g., “I was bothered by things that usually don’t bother me.”] 4-point Likert: 0 = Rarely or none of the time (less than 1 day), 1 = Some or a little of the time (1-2 days), 2 = Occasionally or a moderate amount of time (3-4 days), 3 = Most of the time (5-7 days)]
- Generalized Anxiety Disorder Screener (GAD-7), a 7-item scale designed as a screening and severity measure for generalized anxiety disorder, “Over the *last 2 weeks*, how often have you been bothered by the following problems?” [e.g., “Feeling nervous, anxious, or on edge.”] 4-point Likert: 0 = Not at all, 1 = Several days, 2 = More than half the days, 3 = Nearly every day], includes an additional COVID-19 impact question, “Compared to before COVID-19, how have the frequency and severity of these problems changed during the last 2 weeks?” Sliding scale: 0=Much less, 50 = About the same, 100 = Much more”)
- Snaith-Hamilton Pleasure Scale (SHAPS), a 14-item scale designed to measure the ability to experience pleasure [e.g., “I would enjoy my favorite television or radio program.”] 4-point Likert: 1 = Strongly disagree, 2 = Disagree, 3 = Agree, 4 = Strongly agree])
- Life Orientation Test Revised (LOT-R), a standard psychological tool for measuring optimism consisting of 10 items [e.g., “In uncertain times, I usually expect the best.”] 5-point Likert: 1 = I disagree a lot, 2 = I disagree a little, 3 = I neither agree nor disagree, 4 = I agree a little, 5 = I agree a lot])
- State Optimism Measure (SOM), a 7-item scale capturing in-the-moment optimism [e.g., “I am feeling optimistic about life’s challenges.”] 5-point Likert: 1 = Strongly disagree, 2 = Disagree, 3 = Neither agree nor disagree, 4 = Agree, 5 = Strongly agree)
- Brief State Optimism Measure (BSOM), a two-item questionnaire capturing in-the-moment optimism in regards to longer-term events [e.g., “In thinking about the challenges in my life, I feel RIGHT NOW that ultimately:”] Sliding scale: 0 = Things will get a lot worse, 50 = Things will stay the same, 100 = Things will get a lot better])
- General Self-Efficacy Scale, a 10-item scale measuring self-efficacy [e.g., “I can always manage to solve difficult problems if I try hard enough.”] 4-point Likert: 1 = Not at all true, 2 = Hardly true, 3 = Moderately true, 4 = Exactly true])
- Single-Item Measures of Personality, which consists of five single-item measures with bipolar response scales to measure the Big Five personality traits [e.g., “Generally, I come across as...” with a bipolar response scale between 1 and 9, anchors vary per question])
- Brief COPE, a 28-item scale designed to measure methods of coping with stress [e.g., “I’ve been getting emotional support from others.”] 4-point Likert: 1 = I haven’t been doing this at all, 2 = I’ve been doing this a little bit, 3 = I’ve been doing this a medium amount, 4 = I’ve been doing this a lot])

Participants will be remunerated according to the following remuneration schedule:

Table 2. Remuneration Schedule

Time Point	Survey*
Baseline & Screening	\$25
2-week	\$25
6-week	\$50
3-month	\$25
6-month	\$25
\$150 per participant	
* \$10 for a survey with missed check items	

Payment will be paid by check, where participants will receive a total of five checks, corresponding to the five study assessments occurring at screening, 2-week, 6-week, 3-month and 6-month follow-up. Participants will receive \$25 for each completed online survey, unless they fail to answer 100% of the randomly placed reading alertness check items correctly (e.g.: "Please answer "not at all confident"."), in which case they receive \$10 for a given survey. (Correctly answering all check items is a screening criterion, which is explained to participants during the screening phone call). At the primary endpoint, the 6-week assessment, participants receive an additional \$25 for the survey, because this survey is longer than the other surveys.

Risks are expected to be minimal, and include breach of confidentiality, subject discomfort from answering questions about smoking, and discomfort from quitting smoking. We will minimize these risks by safeguarding electronic data capture by using HIPAA-compliant electronic data capture processes, assuring participants that they do not need to answer any questions they do not want to answer, and by providing information on how to manage smoking cessation.

A subject will be removed from the study if he or she no longer wishes to participate for any reason. A subject may also be removed from the study by the PI, if the participant cannot comply with study procedures (e.g., responds incorrectly to survey check items, cannot install the app on his/her smartphone) or causes undue distress to study staff (e.g., becomes belligerent towards study staff).

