  - e. Use of smoking cessation strategies, as assessed at end of treatment. We hypothesize that SiS > QG > TAU.
  - f. Perceived impact of the provided materials on quitting (e.g., “reminded me to stay on track”), as assessed at end of treatment. We hypothesize that SiS > QG > TAU.
  - g. Appreciation, as measured via the Appreciation Scale at end of treatment. The Appreciation Scale is an 18-item scale which assesses the degree to which one is appreciative. This is an important process outcome for this study, as the SiS app,

unlike the QG app or TAU, emphasizes the experience of positive emotions in order to support smoking cessation. Ten of the items assess frequency of action (e.g., “I do things to remind myself to be thankful” 7-point Likert: 1 = More than once a day, 2 = About once a day, 3 = About once a week, 4 = About once a month, 5 = About once a year, 6 = A few times in my life, 7 = Never). The remaining eight of the items assess level of agreement with appreciative statements (e.g., “I feel that it is a miracle to be alive” 7-point Likert: 1 = Strongly agree, 2 = Agree, 3 = Agree somewhat, 4 = Neither agree nor disagree, 5 = Disagree somewhat, 6 = Disagree, 7 = Strongly disagree). We hypothesize that SiS > QG > TAU.

- h. *(SiS and QG only)* Actual app usage – number of days participants used the assigned app during the prescribed period of app use (i.e., 7 weeks for both apps). Please note that we have a partnership agreement in place with the National Cancer Institute (see attached email) to obtain usage data of the NCI QuitGuide app for our research participants (using de-identified ID numbers), with participants’ explicit permission, as explained in the study facts sheet. We hypothesize that SiS > QG.
- i. *(SiS and QG only)* Self-reported app usage – number of days used app, asked per week; if used, how many minutes per typical day used app
- j. *(SiS and QG only)* Likability rating of the app as measured at end of treatment (i.e., “How much did you like using the smoking cessation app we asked you to use?” 5-point Likert: 1 = I strongly disliked using the app, 2 = I somewhat disliked using the app, 3 = I neither liked nor disliked using the app; 4 = I somewhat liked using the app, and 5 = I strongly liked using the app). We hypothesize that SiS > QG.

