**Analytic Plan.** All successfully enrolled participants (i.e., passed the screening process, was successfully onboarded to the assigned smoking cessation materials) will be included in the outcome analyses. For hypotheses only relevant to the SiS and QG conditions (marked in Specific Aims), only participants successfully onboarded to those conditions will be included in the analyses.

1. **Primary Outcome (Aim 1).** In this proof-of-concept RCT, the primary outcome is self-efficacy to abstain from smoking, as measured by the SEQ-12. The primary endpoint is end-of-treatment, which occurs 6 weeks after the originally chosen quit day. To test for differences between randomized groups, we will fit a fixed effects repeated measures model using PROC MIXED, where observations are modeled as nested within persons. Predictors included in the model will be GROUP (i.e., SiS vs. QG vs. TAU), TIME (i.e., BL, Week 2, Week 6, Week 12 and Week 24), and the GROUP\*TIME interaction effect. A contrast statement will be used to derive the test statistic for the GROUP comparison at Week 6, our primary endpoint, given the overall longitudinal model. This contrast statement will test the null hypothesis that SiS = QG = TAU. If this null hypothesis is rejected ( $p<0.05$ ), we will conduct pair-wise follow-up tests that compare the three possible pairwise comparisons (i.e., SiS vs. QG, SiS vs. TAU, and QG vs. TAU).
2. **Secondary Outcomes (Aim 2).** The secondary outcomes in this proof-of-concept RCT are exploratory. Thus, we will not correct for multiple testing. We will fit one model per secondary outcome, using an alpha of 0.05 for all analyses.
  - 2.1. To test for differences between randomized groups for outcomes that are assessed multiple times (Aims 2a, 2b), our overall modeling approach will be the same as for Aim 1. That is, for each outcome, we will fit a fixed effects repeated measures model, where observations are modeled as nested within persons. Predictors included in the model will be GROUP, TIME, and the GROUP\*TIME interaction effect. However, for these secondary outcomes, the definitions of the TIME effect varies across these secondary outcomes, based on their assessment schedule. The distribution of the outcome variables also varies across these variables. Thus, we will implement this overall modeling approach for these variables as follows:

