- 2.2. To test for differences between randomized groups for outcomes that are only assessed at end of treatment (Aims 2c – 2l), for each outcome, we will use a fixed effects model, where GROUP is the only predictor, and score at end of treatment is the dependent variable. Histograms will be used to guide selection of the most appropriate distribution. We anticipate that we will use the normal distribution for the CSQ-8 (Aim 2c), use of strategies (Aim 2e), perceived impact (Aim 2f), the AS (Aim 2g), actual app usage (Aim 2h), self-reported app usage (Aim 2i), likeability of the app (Aim 2j), satisfaction with the app (Aim 2k), and the SUS (Aim 2l), as implemented via the PROC MIXED procedure in SAS. We anticipate that we will use the Poisson distribution for time spent applying content (Aim 2d), as implemented via the PROC GENMOD procedure in SAS. If the GROUP effect is statistically significant ( $p<0.05$ ), we will conduct pair-wise follow-up tests that compare the three possible pairwise comparisons (i.e., SiS vs. QG, SiS vs. TAU, and QG vs. TAU). These follow-up analyses will not be necessary for secondary outcomes that are only assessed for the SiS and QG conditions (i.e., Aims 2j-2l).
3. Exploratory mediational models (Aim 3): We will use mediational modeling, using the product-of-coefficients approach and a fully lagged model to test if hypothesized within-person changes (see Figure 1) occur, and if they are linked to subsequent abstinence. The independent variable will be randomized group assignment (i.e., SiS vs. TAU), and the outcome variable will be self-reported 30-day point prevalence abstinence as measured at 6-month follow-up). The mediators will be our theorized mechanisms of change, as listed in the Aim 3 (i.e., self-efficacy, emotional well-being, desire to smoke, breadth of thought-action-repertoire, processing of processing of self-relevant health information.). Baseline values on these constructs will be included in the model to control for individual differences

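### The Appreciation Scale (Aim 2g) has no baseline and is compared at Week 6 with GROUP alone, which gives up precision that well-being scales already collected before randomisation could supply

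*Combined protocol and SAP*

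**What the plan says.** Aim 2g (Section II) lists appreciation as a secondary outcome, measured "at end of treatment. The Appreciation Scale is an 18-item scale which assesses the degree to which one is appreciative". It gives the scale special standing, "This is an important process outcome for this study", because SiS, unlike the two control conditions, puts positive emotion at the centre of its support.

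In Table 1 (Section V) the row beginning "Appreciation Scale (AS" carries one mark. Aim 2g and Analytic Plan 2.2 both place that assessment at end of treatment, so it is Week 6. The same table shows PANAS, SWLS and SHS at baseline and at every follow-up.

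Analytic Plan 2.2 (Section VI) puts Aims 2c to 2l under one model, "where GROUP is the only predictor, and score at end of treatment is the dependent variable". Analytic Plan 2 adds: "The secondary outcomes in this proof-of-concept RCT are exploratory". There is no multiplicity correction, and the plan fits one model per outcome, "using an alpha of 0.05 for all analyses".

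**The concern.** Most outcomes under Analytic Plan 2.2 concern the assigned materials: satisfaction with them, their perceived impact, their usability, how much they were used. These cannot have a baseline, so a model with GROUP alone is natural. The Appreciation Scale is different. It describes the person, and some of its response options refer to long periods ("5 = About once a year, 6 = A few times in my life, 7 = Never"). Part of the variation in the Week 6 score is therefore likely to have been present before randomisation.

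The plan removes such variation elsewhere. The Aim 3 models include baseline values of the mediators to account for individual differences, and Aim 2b analyses change from baseline. For Aim 2g nothing is removed, although related constructs are measured in the screening survey, which comes before the enrolment call at which participants are randomised (Section IV). At stake is the width of the interval around the arm difference for this outcome, and whether a Week 6 difference is described correctly when it is reported.

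**Working it through.** **Inputs from the documents.** Planning effect d=0.50, 64 evaluable and 75 enrolled per group, 85% retention (Section VI, Statistical Power; d refers to the primary outcome, not to the Appreciation Scale). Alpha 0.05 (Analytic Plan 2). Allocation 1:1:1 (Section IV).

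**Assumed.** Two-sided testing and 80% power, because neither is stated. Multiple correlation R between baseline SHS, SWLS and PANAS positive affect and the Week 6 Appreciation score: 0.3 to 0.6. The documents give no correlation, SD, reliability or expected effect for this scale.

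**Step 1: reproduce the plan's sample size.** A two-sample t-test with d=0.50, two-sided 0.05 and 80% power needs 63.77 per group, so 64. Power at 64 is 80.1%. One-sided testing (50 per group) or 90% power (85 per group), each by normal approximation, does not match. Retention: 75 × 0.85 = 63.75, which agrees with 64 to within rounding. The stated size is thus that of an unadjusted two-arm comparison.

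**Step 2: the Aim 2g model as planned.** In SD units, the standard error of a pairwise difference is sqrt(2/64) = 0.177. Power is 80% at d=0.50, 39% at d=0.30 and 20% at d=0.20. The smallest effect detectable with 80% power is 0.50.

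**Step 3: with baseline covariates.** Residual variance is multiplied by (1 − R²), and the detectable effect becomes 0.50 × sqrt(1 − R²).

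| R | Variance removed | SE of difference | Detectable d (80% power) | Power at d=0.50 | Power at d=0.30 | Equivalent unadjusted n per arm |
|---|---|---|---|---|---|---|
| none | 0% | 0.177 | 0.50 | 80% | 39% | 64 |
| 0.3 | 9% | 0.169 | 0.50 × sqrt(0.91) = 0.48 | 84% | 42% | 64/0.91 = 70 |
| 0.6 | 36% | 0.141 | 0.50 × sqrt(0.64) = 0.40 | 94% | 56% | 64/0.64 = 100 |

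**Step 4: the cost.** With 3 × 64 = 192 evaluable participants, residual degrees of freedom go from 192 − 3 = 189 to 189 − 3 = 186. The effect on the critical value is negligible.

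**Limit of these figures.** They are pairwise. Analytic Plan 2.2 first requires a significant three-group test. Its unadjusted power, when the largest difference is d=0.50, is about 71% to 83%, depending on where the middle arm lies.

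**The case against.** The case for leaving the plan alone is substantial. The outcome is secondary and declared exploratory. Randomisation makes the unadjusted Week 6 contrast unbiased in expectation, apart from dropout. The between-person SD is already the denominator of d, so this comparison has the same 80% pairwise power at d=0.50 as the plan's own sample size calculation. Positive affect and well-being are also followed from baseline by PANAS, the happiness items, SWLS and SHS, and the Appreciation Scale is not among the Aim 3 mediators. All of this stands. It limits the point to precision and reporting, but does not explain why covariates already in hand should go unused.

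A reader might go further in four ways, and the documents do not support any of them.

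- *That stable differences between persons overwhelm the arm contrast.* They widen its standard error, and that is already counted in the 80% power.
- *That a true effect would probably be missed.* Power is low for small effects (39% at d=0.30), but no expected effect is stated for this scale.
- *That chance imbalance cannot be told apart from a treatment effect.* The standard error and p-value already allow for chance imbalance. Adjustment makes the test sharper, but its absence does not make the test invalid.
- *That the scale is a fixed trait.* Its frequency options also include daily and weekly, ten of its 18 items ask about frequency of action, and SiS assigns daily exercises. Scores may well move in seven weeks.

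**Conclusion.** The point holds as a modest, avoidable loss of precision. An outcome that the protocol singles out is measured once, and the planned model ignores related measures taken before randomisation. Adjustment would remove 9% to 36% of residual variance and lower the detectable pairwise effect from d=0.50 to about 0.48 to 0.40. This rests on an assumed R of 0.3 to 0.6, two-sided 0.05, 80% power and 64 evaluable per arm. At the low end the gain is small.

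No bias in the planned contrast is claimed, other than what dropout may cause in any analysis of this kind. Because there is no baseline Appreciation score, the analysis can support a statement about a difference between arms at Week 6, but not one about change in appreciation.

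**What to change.** In Analytic Plan 2.2, name baseline SHS, SWLS and PANAS positive affect as covariates in the Aim 2g model, for all participants, and do so before outcome data are examined so that the choice is not driven by the data. State that the result will be reported as an adjusted between-arm difference at Week 6, not as change. This needs no new data and costs three degrees of freedom.

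A baseline Appreciation Scale would probably predict the Week 6 score better: at an assumed correlation of 0.5 to 0.8, the detectable effect would be 0.50 × sqrt(0.75) = 0.43 to 0.50 × sqrt(0.36) = 0.30. It is worth adding only if it can be collected from essentially all participants before randomisation. Adding it for later enrollees alone would leave it missing for everyone enrolled before, and would put different covariates in one model. The document is dated January 2022 and the funded project dates end in June 2021, so it may already be too late.
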